Three months of first-line OA treatment delivered either face-to-face or digitally with a program adherence of 80% or higher. The choice of this cut-off was based on recommendations in the Swedish Guidelines for management of knee and hip osteoarthritis by the National Board of

Health and Welfare. Adherence defined as $\geq 80\%$ completed education videos, exercises and questionnaires offered in the digital program and participation in two out of three educational lessons and at least 10 of the 12 supervised group exercise sessions offered in the BOA program.

Main outcome

Main outcome will be self-reported change in pain on the NRS-scale between baseline and three months follow-up. The NRS comprises an 11-point scale where 0 indicates no pain and 10 indicates the worst possible pain [13] (Table 1).

Secondary outcomes

Secondary outcomes will be change in self-reported walking difficulties (dichotomous reply, yes/no), willingness for joint surgery (dichotomous reply, yes/no) and health-related quality of life, assessed with the EuroQol – 5 dimension descriptive system (EQ-5D-3L)[14] between baseline and three months follow-up (Table 1).

Sample size

As this study aims at estimating treatment effects, the important issue to assess is not power (related to a hypothesis), but precision – i.e. the width of the confidence interval. To illustrate this, consider the example of an RCT to compare mean joint pain after exercise intervention for OA, between persons that receive the treatment in different modalities. The minimum clinically important difference is typically considered one unit on a 0-10 NRS scale. To obtain a 95% confidence interval for the between-group difference with a width of at most 0.5 units (i.e. very precise) in a sample with a typical standard deviation of 1.5, with 99% probability, we will need ~ 630 patients in total. Considering our cohort size of >2000 persons who underwent the intervention, we will be able to estimate between-group differences also in subgroups, by sex, BMI, etc.

Statistical analysis

In this study we will use observational data to emulate an equivalence trial comparing the effect on joint pain of a digitally delivered first-line intervention and of an in-person delivered first line intervention for people with OA of the hip or knee.

Main outcome analysis

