The main outcome will be analyzed using a propensity score matching approach [17]. We will estimate the propensity score using a logistic regression model, in which we will regress the treatment status on the observed baseline characteristics of the participants. The characteristics to include in the propensity score will be selected using the disjunctive cause

criteria [16], including factors in the analysis identified as causes of treatment allocation(exposure) and/or the pain change (outcome) (Table 2). We will use nearest neighbor matching to select controls (BOA participants) whose propensity score is closest to that of the treated subject. Furthermore, we will use an optimal matching strategy to minimize the total within-pair difference of the propensity score. Within-pair differences in main outcome will be analysed using a paired t-test. Finally, we will adjust the analysis for baseline pain using linear regression in order to increase the precision of the estimates and minimize the regression to the mean effect [17, 18].

Assessing propensity score balance

Balance of baseline variables between treated and control subjects in the matched study population will be assessed using standardized difference [19].

Equivalence bounds

In order to establish equivalence between the interventions the pain change after the intervention should differ of less than 1-point on a 0-10 NRS pain scale. This cut off was selected based on previous work identifying 1-point change as the MCID in people with OA [20].

Sensitivity analysis

In order to evaluate and contrast the influence of choice of analysis method on study results, linear regression analysis based on the same adjustment set used for the propensity score, representing the causal effect studied, will be applied and both adjusted and unadjusted estimates will be presented, discussed and contrasted against results from the propensity score matched analysis.

Missing data

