Age	Confounder	Yes
Sex	Confounder	yes
Weight	Confounder	yes
Height	Confounder	yes
Education level	Confounder	yes
Working status	Confounder	yes
Most affected Joint	Confounder	yes
Other affected joints	Confounder	Yes (used as number of joints)
On Waiting list for surgery	Confounder	No (very rare)
Wish for surgery	Secondary outcome	yes
Physical activity (training)	Confounder	yes
Physical activity (every-day exercise)	Confounder	yes
Overall health	Confounder	yes
Walking difficulties	Secondary outcome	yes
Pain	Outcome	Yes (baseline pain)
EQ-5D	Outcome	
Fear of movement	Confounder	yes
Compliance with the intervention	Inclusion criteria	No
Previous surgery index joint	Confounder	No

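### Walking difficulties and willingness for surgery are defined as change in a yes/no reply with no comparison model named; the 3-month reply adjusted for the baseline reply would be modestly more precise

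*SAP*

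**What the plan says.** Under Secondary outcomes the SAP states: "Secondary outcomes will be change in self-reported walking difficulties (dichotomous reply, yes/no), willingness for joint surgery (dichotomous reply, yes/no". The period is baseline to three months. The SAP does not say how a change in such a reply is coded.

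The comparison methods stand under Main outcome analysis and concern pain. The matched comparison is given as: "Within-pair differences in main outcome will be analysed using a paired t-test". A regression step follows it, with baseline pain as the covariate and a gain in precision as one of its stated aims.

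Three other places bear on the point:

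- Table 1 marks both baseline replies as used for matching: "Walking difficulties Secondary outcome yes" and "Wish for surgery Secondary outcome yes".
- The sensitivity analysis is a "linear regression analysis based on the same adjustment set used for the propensity score". By Table 1, that set includes both replies. The section does not say that it covers the secondary outcomes.
- Balance is checked after matching: "Balance of baseline variables between treated and control subjects in the matched study population will be assessed using standardized difference". No threshold or remedy is given.

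**The concern.** A person's change in a yes/no reply can only be improved, unchanged or worsened. Unchanged pools those who stayed at 'yes' with those who stayed at 'no', and someone who answers 'no' at baseline cannot improve. Whether change is scored per person or read as a change in the proportion answering 'yes', the group contrast is the same number: the 3-month difference minus the whole baseline difference.

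Subtracting the whole baseline difference removes too much when the two replies are only moderately correlated. The excess adds variance, and any imbalance that matching leaves behind enters the contrast with the opposite sign. For pain, the SAP deals with this by adjusting for the outcome's own baseline value, to gain precision and limit regression to the mean. It states no counterpart for the two yes/no outcomes. At stake are the width of their confidence intervals and some protection against residual imbalance.

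**Working it through.** **The plan's own figure.** The Sample size section gives about 630 patients for a 95% CI of width at most 0.5 NRS units, SD 1.5, with 99% probability. Taking the smallest n per arm for which 2·t(0.975, 2n−2)·S·√(2/n) ≤ 0.5 with probability 0.99 gives 632 in total, so the figure reproduces. It concerns pain and says nothing on the yes/no outcomes.

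**Inputs.** The SAP gives no reply rates or correlations. All of these are assumptions: baseline 'yes' p0 of 25-80%, 3-month 'yes' p1 of 20-65%, correlation r of 0.3-0.6, and 1000 per arm (the SAP says only that the cohort exceeds 2000).

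**Formulas.** With v0 = p0(1−p0), v1 = p1(1−p1) and b = r·√(v1/v0):

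- variance of change, per person: v0 + v1 − 2r·√(v0·v1)
- variance of the 3-month reply given the baseline reply: v1(1−r²)
- 95% CI half-width: 1.96·√(2·variance/n)
- shift of the change contrast from a leftover baseline imbalance d: (b−1)·d

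**One case in full** (50% to 40%, r = 0.5). v0 = 0.25, v1 = 0.24, √(v0·v1) = 0.2449.

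- Change: 0.49 − 0.2449 = 0.2451
- Adjusted: 0.24 × 0.75 = 0.18
- Ratio: 0.18/0.2451 = 0.73
- Half-widths: 4.34 and 3.72 points
- b = 0.49, so d = 5 points shifts the change contrast by −0.51 × 5 = −2.6 points

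**All 15 cases** (each a feasible joint distribution; entries are for r = 0.3 / 0.5 / 0.6):

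| p0 to p1 | Variance ratio, adjusted/change | Half-width in points, change vs adjusted | Shift in points for d = 5 |
|---|---|---|---|
| 80% to 65% | 0.76 / 0.87 / 0.92 | 4.58 vs 3.99 / 3.89 vs 3.62 / 3.49 vs 3.34 | −3.2 / −2.0 / −1.4 |
| 70% to 60% | 0.69 / 0.80 / 0.85 | 4.92 vs 4.10 / 4.16 vs 3.72 / 3.73 vs 3.44 | −3.4 / −2.3 / −1.8 |
| 50% to 40% | 0.64 / 0.73 / 0.78 | 5.13 vs 4.10 / 4.34 vs 3.72 / 3.88 vs 3.44 | −3.5 / −2.6 / −2.1 |
| 30% to 25% | 0.61 / 0.71 / 0.75 | 4.63 vs 3.62 / 3.91 vs 3.29 / 3.50 vs 3.04 | −3.6 / −2.6 / −2.2 |
| 25% to 20% | 0.60 / 0.69 / 0.73 | 4.33 vs 3.34 / 3.66 vs 3.04 / 3.28 vs 2.80 | −3.6 / −2.7 / −2.2 |

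The variance falls by 8-40% and the half-width by about 0.2-1.0 points.

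**Effect of matching.** These variances treat the members of a pair as independent. The excess variance of change is (1−b)²·v0; in the worked case, 0.51² × 0.25 = 0.065 = 0.245 − 0.18. If the baseline replies within pairs have correlation k, and each 3-month reply depends on its own baseline reply only, the excess becomes (1−k)·(1−b)²·v0. It vanishes when every pair shares the reply, because the baseline terms then cancel. Matching is on one score built from the 15 variables that Table 1 marks for matching, so k is unknown but need not be near 1.

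**Would baseline pain serve instead?** A simulation of 2000 runs assumed 80% to 60%, r = 0.5, a 4-point imbalance, 1000 per arm and a pain-reply correlation of 0.4. The bias was −1.6 points unadjusted, −1.4 adjusted for baseline pain, and about 0 adjusted for the baseline reply.

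**The case against.** The strongest reply is that the SAP never says it will analyse these outcomes by raw change with adjustment for pain alone. A reader might infer that baseline pain is the only adjustment in the plan. The documents do not support that: both replies are matching variables, both fall within the sensitivity regression's adjustment set, and balance is checked. This stands. The gap is that no model is named for these outcomes and the sensitivity regression is not expressly extended to them.

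A reader might also infer that these comparisons will be biased. That too goes beyond the text. The shift needs an imbalance that survives matching, and 5 points is generous. At 1000 per arm the chance SE of a difference in baseline proportions, √(2·v0/1000), is 1.8-2.2 points for 25-80% 'yes'. Five points is therefore 2.2-2.8 standard errors even without matching.

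Finally, in non-randomised data neither method is right by default. If a leftover group difference is stable over time, change removes it and baseline adjustment does not. This stands as a matter of assumption. But the SAP has already chosen baseline adjustment for pain, citing regression to the mean, and the same choice here would be consistent.

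**Conclusion.** The point holds in a limited form. The SAP defines two secondary outcomes as change in a yes/no reply, leaves the coding open and names no comparison for them. A raw change contrast would give up 8-40% of its variance relative to the adjusted 3-month comparison, or about 0.2-1.0 percentage points of half-width at 1000 per arm. It would also pass on 28-72% of any leftover imbalance with reversed sign (the 1.4-3.6 points in the table divided by 5).

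These sizes rest on assumed rates, correlations and arm size, and on independent replies within pairs. The tighter the matching on the reply, the smaller the gain. The bias is conditional and probably small after matching.

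A reader might extend the point to the main conclusion. The hypothesis and the equivalence bounds concern pain change, so they are not affected. Severity is minor.

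**What to change.** Under Secondary outcomes, define walking difficulties and willingness for surgery as the reply (yes/no) at 3 months. Under Statistical analysis, add wording such as:

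> Each dichotomous secondary outcome at 3 months will be compared between the matched groups as a risk difference with 95% CI, from a regression with treatment and the baseline reply to the same question as covariates and standard errors clustered on the matched pair.

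Counts of improved, unchanged and worsened can stay as description.

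The cost is two sentences and one model per outcome, with no new data, since Table 1 shows that both registers hold the replies. The small downside is that the result is a covariate-adjusted risk difference and not a raw change in percentages.

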The study was approved by the regional ethics committee of the Swedish Ethical Review Authority (Dnr 2019-06288, decision date 2020-02-11 and is pre-registered at ClinicalTrials.gov (NCT04836988). Participants were informed that data generated from the register may be used for research purposes at registration (BOA) or provided digital informed consent for the same purpose at registration (JA). The study adheres to the STROBE guidelines for observational studies.

Data sources

BOA (face-to-face): The BOA registry was started in 2008 and currently includes more than 100,000 individuals with OA who have registered for an evidence-based self-management program, including education, exercise and weigh management if needed at a primary care clinic.

Joint Academy (digital program): The digital self-management program started in 2014 and was originally inspired by the Swedish evidence based face-to-face BOA self-management treatment program [9]. The associated registry currently includes more than 30 000 individuals with OA. The intervention consists of a digital OA self-management program (Joint Academy®) [11, 12] comprising text lectures on OA with accompanying quizzes, physical activity and self-management in OA. The participant also receives exercises aiming at improving strength and neuromuscular control of various levels based on each individuals' progression in the program.

Data extractions and linkages

All data extracted from the digital self-management program (JA) and BOA registries. Criteria for inclusion in the data extraction are:

- Clinical diagnosis of OA, with knee or hip OA as their index (most symptomatic) joint
- Enrolled in either of the two programs between April 1, 2018 and December 31, 2019
- Provided 3-month follow-up data for the main outcome on or before March 31, 2020
- Program adherence of 80% or higher.

The data from the two registers will be linked using personal identity numbers to identify individuals that may have participated in both programs during the specific time window. Patients that participated in both programs will be excluded from further analysis.

The JA participants will be matched 1:1 to participants in the BOA register using the propensity scoring approach described below.

Main exposures and outcomes

Exposures

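### The matched primary analysis adjusts only for baseline pain, so imbalance that matching leaves in the other covariates passes into the treatment difference

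*SAP*

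**What the plan says.** - **Who is matched** (Data extractions and linkages): "The JA participants will be matched 1:1 to participants in the BOA register using the propensity scoring approach described below".
- **How** (Main outcome analysis): "We will use nearest neighbor matching to select controls (BOA participants) whose propensity score is closest to that of the treated subject". In addition, "we will use an optimal matching strategy to minimize the total within-pair difference of the propensity score". Both rules rank distances. No caliper, common-support restriction, replacement rule or provision for leaving a JA participant unmatched is stated.
- **Analysis of the pairs** (Main outcome analysis): "Within-pair differences in main outcome will be analysed using a paired t-test". Then "we will adjust the analysis for baseline pain using linear regression in order to increase the precision of the estimates" and to limit regression to the mean. No other covariate is named for this regression.
- **Balance** (Assessing propensity score balance): baseline variables "in the matched study population will be assessed using standardized difference". No threshold or action is given.
- **Covariates** (Table 1): besides baseline pain, 14 variables are marked for matching: age, sex, weight, height, education, working status, index joint, number of other joints, wish for surgery, two physical activity items, overall health, walking difficulties and fear of movement.
- **Sensitivity analysis**: a linear regression on the same adjustment set is contrasted with the matched result.
- **Missing data**: with 5% or more missing, the primary analysis changes from matching to linear regression. The complete-case branch carries the same 5% condition, evidently a slip for less than 5%. This point concerns the branch in which matching stays primary.

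**The concern.** Nearest-neighbor matching picks the best partner available, and optimal matching minimises the summed distance. Neither ensures that a given pair is close. If good BOA partners run short, the matched groups still differ on some covariates, and a later step has to deal with that. Here none does: the paired t-test has no covariates, the regression has only baseline pain, the balance check triggers nothing, and the full-covariate regression is only a sensitivity analysis.

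The primary result is an equivalence claim against 1 NRS point, from a study planned for a narrow confidence interval. Residual confounding shifts the centre of that interval without widening it. The shift can go either way: it can suggest a difference that is not there, or hide part of a real one.

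**Working it through.** **Inputs from the SAP.** SD 1.5, 95% CI of full width at most 0.5 with 99% probability, about 630 patients in total (Sample size); margin 1 point (Equivalence bounds); 1:1 matching and baseline-pain adjustment (Main outcome analysis).

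**Step 1: the plan's own figure.** Take the smallest n per group with P(2·t(0.975, 2n−2)·s·√(2/n) ≤ 0.5) ≥ 0.99, where s² follows its chi-square distribution around 1.5². This gives n = 316, or 632 in total, which reproduces about 630. The calculation covers sampling error only and makes no allowance for bias.

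**Step 2: what unadjusted imbalance does.** With a linear outcome model, bias ≈ Σ (slope of covariate k) × (mean difference left in covariate k).

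Assumed settings, none from the SAP: 400 digital participants; five independent confounders, each shifted by d SD between programs; slope 0.3/√5 NRS points per SD for each; baseline pain balanced, independent of the others, slope −0.5; residual SD 1.4; true treatment effect 0. The outcome variance within a program is 0.09 + 0.25 + 1.96 = 2.30, so the SD is 1.52, close to the plan's 1.5. The five confounders explain 0.09/2.30 = 4% of it.

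If the pools are equal and matching is without replacement, everyone is retained and the full shift d remains. The expected bias is then 5 × (0.3/√5) × d = 0.67d, which is 0.13, 0.20 and 0.34 for d = 0.2, 0.3 and 0.5.

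**Step 3: simulation.** Logistic propensity score, optimal 1:1 matching without replacement, 25 runs per cell. The Monte Carlo error is about 1.5·√(2/400)/√25 = 0.02. Entries are mean estimates in NRS points; the true value is 0.

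| BOA:JA | d | Baseline pain only (plan) | All matching covariates | Baseline pain only, caliper 0.2 SD of logit | JA dropped by caliper |
|---|---|---|---|---|---|
| 1 | 0.2 | 0.15 | 0.01 | 0.02 | 14% |
| 1 | 0.3 | 0.23 | 0.02 | 0.02 | 22% |
| 1 | 0.5 | 0.33 | 0.00 | 0.04 | 38% |
| 1.5 | 0.2 | 0.01 | −0.01 | 0.00 | 3% |
| 1.5 | 0.3 | 0.06 | 0.00 | 0.01 | 9% |
| 1.5 | 0.5 | 0.17 | −0.01 | 0.01 | 24% |
| 3 | 0.2 | 0.04 | 0.04 | 0.04 | <1% |
| 3 | 0.3 | 0.02 | 0.01 | 0.01 | 1% |
| 3 | 0.5 | 0.05 | −0.02 | 0.00 | 9% |

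At 8:1 the plan's bias was 0.03 or less in size for every d. The equal-pool rows agree with Step 2 within Monte Carlo error. The 0.04 at 3:1 and d = 0.2 is the same in all three analyses, so it is simulation noise rather than imbalance.

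**Step 4: effect on the equivalence decision.** Assume that a two-sided 95% CI is judged against the margin.

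- True difference 0, 400 pairs: half-width = 1.96 × 1.5 × √(2/400) = 0.21. With bias 0.33 the interval is about 0.12 to 0.54. It lies inside the margin, so equivalence is still declared, but it wrongly excludes zero.
- True difference 1, bias b towards zero, 316 per group: SE = 1.5·√(2/316) = 0.119. The chance of declaring equivalence is Φ(b/0.119 − 1.96), nominally 2.5%. For b = 0.05 it is Φ(−1.54) = 6%; for 0.15, Φ(−0.70) = 24%; for 0.33, Φ(0.81) = 79%.

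**The case against.** **The SAP nowhere rules out a caliper.** A reader might infer that every digital participant must be paired however poor the match. The text does not support that as a rule: it is silent on calipers, common support and replacement. The gap is an omission. It still matters, because nothing stated limits the pair distance.

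**The BOA pool is probably larger.** Data sources gives more than 100,000 registered in BOA and more than 30 000 in JA, about 3.3:1, where the simulated bias is near noise. This stands as a reason for caution about size, but it does not settle the matter. The counts cover whole registries that began in 2008 and 2014, before the enrolment window, the follow-up requirement and the adherence rules. Both programs face an adherence filter. Sample size gives only a cohort above 2000, not split by program.

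**Large biases come from assumed corners.** Equal pools, six covariates explaining 20% of pain-change variance and programs 1 SD apart gave 0.56 in a separate simulation. None of those settings is in the SAP. Even then, with a true difference of zero and 400 pairs, 0.56 + 0.21 = 0.77 is inside the margin. A reader might infer that the plan is likely to reach a wrong equivalence conclusion. The documents do not support this: a false claim needs a true difference near or above 1 point together with bias towards zero.

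**The plan already exposes the problem.** The sensitivity regression uses the full adjustment set. With equal pools matched without replacement, it is in effect the proposed fix, so a conflict would show. This stands in part: the conflict would be visible, but the primary estimate would be unchanged and no rule says which result prevails.

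**The simulation favours the fix.** Its outcome model is linear, so full adjustment succeeds by construction. Its baseline pain is unrelated to the other covariates; if they are related, the planned adjustment would remove some of the bias. Both limits are accepted.

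**Conclusion.** The concern holds in a limited form. While matching is primary, the plan has no step that removes imbalance left in the matching covariates other than baseline pain, so that imbalance enters the primary treatment difference. This follows from the text and needs no assumption.

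The size is uncertain. Under the assumed settings it is about a seventh to a third of the 1-point margin with equal pools, and at most a twentieth at 3:1 or more. The eligible ratio and the overlap decide which applies, and neither is given. The point is worth acting on because the correction is nearly free, not because a large bias has been shown.

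**What to change.** 1. In Main outcome analysis, extend the post-match linear regression from baseline pain to all covariates marked yes for matching in Table 1. State that this estimate and its confidence interval are the ones compared with the 1-point margin. The cost is one sentence in the SAP and a longer model formula; no participant is dropped. The downside is reliance on a roughly correct outcome model where overlap is poor.
2. Optionally, report the distribution of pair distances and repeat the analysis within a stated caliper as a sensitivity analysis, with the number and characteristics of unmatched JA participants. The illustrative 0.2-SD caliper is a convention, not an SAP figure. It dropped 14% to 38% of JA participants in the equal-pool simulations, so the SAP should say that the result then applies only to digital participants with comparable BOA patients.

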2022-04-14

**FACE TO FACE OR DIGITALLY? A COMPARISON OF FIRST-LINE INTERVENTIONS DELIVERY FOR
PEOPLE WITH HIP OR KNEE OSTEOARTHRITIS (NCT04836988)**

Background

Osteoarthritis (OA) is among the leading causes of disability worldwide and due to its raising prevalence, the identification of appropriate care and care delivery modalities is a priority for the health care systems [1, 2]. Exercise and education constitute the first-line intervention for people with knee and hip OA and have been shown to be effective regardless of symptoms and disease severity [3, 4]. Unfortunately, there is a discrepancy between recommended treatment and what patients receive. Less than 40% of people with OA seeking care seem to receive recommended first line management internationally [5]. To implement those guidelines, the Better Management of Patients with OsteoArthritis (BOA), a face-to-face concept including education and an option to exercise, has been developed and are offered at primary care clinics in Sweden since 2008 [6]. However, traditional face to face interventions present barriers, such as limited access and lack of flexibility, which may limit the patients' adherence with the interventions [7]. Digital delivery of the management program may be one way of overcoming such barriers [8, 9]. In light of the current Covid-19 pandemic, digitally delivered treatments may gain even further awareness as a feasible treatment option. Both delivery methods have been reported to reduce OA symptoms in patients with hip and/or knee OA [10, 11], but little is known whether the results of digital interventions are comparable with traditional face-to-face rehabilitation programs.

Aim

To compare the outcomes (average treatment effect) of two different modalities of first-line treatment delivery (face-to-face vs. digitally) after 3 months of program participation.

Hypothesis

There will be no difference in the average treatment effect of the main outcome between the two delivery methods.

Methods

This is a retrospective observational registry-based study comparing outcomes of a face-to-face and a digital OA management program.

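### No planned analysis allows for correlation among face-to-face patients of the same clinic, so the reported 95% interval is likely somewhat too narrow if several matched patients share a clinic

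*SAP*

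**What the plan says.** Under Main outcome analysis the SAP states: "Within-pair differences in main outcome will be analysed using a paired t-test". It continues: "Finally, we will adjust the analysis for baseline pain using linear regression in order to increase the precision of the estimates". The Sensitivity analysis section adds linear regression on the same adjustment set. The Missing data section switches the primary analysis to linear regression with multiple imputation when missing data reach 5%. None of these names a clinic or group effect, a random effect or a cluster-robust variance. Table 1 lists no clinic variable.

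The two programmes are described differently. Under Data sources, BOA offers "education, exercise and weigh management if needed at a primary care clinic", and under Exposures an included BOA patient must have attended "at least 10 of the 12 supervised group exercise sessions offered in the BOA program". The digital programme gives "exercises aiming at improving strength and neuromuscular control of various levels based on each individuals' progression in the program"; no grouping is described.

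The design is one-to-one: "The JA participants will be matched 1:1 to participants in the BOA register". Under Equivalence bounds, "the pain change after the intervention should differ of less than 1-point on a 0-10 NRS pain scale". No interval or confidence level is tied to that bound.

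**The concern.** A paired t-test takes the within-pair differences as independent of each other. Propensity-score matching does not secure this. Two BOA patients from one clinic fall into different pairs, so anything that clinic or its exercise group adds to the pain change is common to both differences. With a positive ICC the variance of the mean difference then exceeds what the t-test computes. The regressions have the same gap, because they treat patients as independent.

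The direction is unfavourable. An interval that is too short makes equivalence easier to declare, and the Sample size section says that precision, meaning interval width, is the important issue in this study. The point estimate is not in question.

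**Working it through.** **Inputs from the SAP.** SD 1.5, 95% confidence, total width at most 0.5 with 99% probability, about 630 patients in total, a cohort of more than 2000, 1:1 matching, margin 1 point.

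**Assumptions, because the SAP gives no values.** ICC 0.01 to 0.05; *m* = 3 to 20 matched BOA patients per clinic, equal across clinics; clustering in the BOA arm only; no correlation between the two members of a pair; about 1000 pairs, reading the 2000 as both arms together.

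**Step 1: the plan's own figure.** For *n* independent patients per arm, the width is 2 × t(0.975, 2n−2) × s × √(2/n). It is at most 0.5 with probability 0.987 at n = 314, 0.989 at n = 315 and 0.991 at n = 316. The smallest n that reaches 99% is 316, or 632 in total, which agrees with the stated figure. Without the 99% requirement, n = 2 × (1.96 × 1.5 / 0.25)² = 276.6, so 277 per arm and 554 in total. The stated figure therefore contains no allowance for clustering.

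**Step 2: effect of clustering in one arm.** The design effect in the BOA arm is DE = 1 + (m − 1) × ICC. The true standard error is the naive one times f = √((1 + DE)/2). The naive one is understated by 1 − 1/f, and the nominal 95% interval covers 2Φ(1.96/f) − 1.

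| m | ICC | DE | f | SE understated by | True coverage | Half-width, 1000 pairs |
|---|---|---|---|---|---|---|
| 3 | 0.01 | 1.02 | 1.005 | 0.5% | 94.9% | 0.132 |
| 3 | 0.05 | 1.10 | 1.025 | 2.4% | 94.4% | 0.135 |
| 5 | 0.01 | 1.04 | 1.010 | 1.0% | 94.8% | 0.133 |
| 10 | 0.02 | 1.18 | 1.044 | 4.2% | 94.0% | 0.137 |
| 10 | 0.05 | 1.45 | 1.107 | 9.7% | 92.3% | 0.146 |
| 20 | 0.05 | 1.95 | 1.214 | 17.6% | 89.3% | 0.160 |

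The naive half-width is 1.96 × 1.5 × √(2/1000) = 0.131. In the last row it becomes 1.96 × 1.5 × √(2.95/1000) = 0.160.

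**Step 3: effect on the equivalence verdict.** Suppose that equivalence is read as the 95% interval lying within ±1, which the SAP does not state. The largest observed difference that still passes is 1 − 0.131 = 0.869 with the naive interval and 1 − 0.160 = 0.840 in the last row. Only a result between about 0.84 and 0.87 would be judged differently. Under the same reading, if the true difference were exactly 1 point, the error rate at that bound would rise from 2.5% to 3.8% (m = 10, ICC 0.05) or 5.3% (m = 20, ICC 0.05).

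**Step 4: at the planning size.** With 315 per arm the expected total width is 2 × 1.96 × 1.5 × √(2/315) = 0.47. It becomes 0.52 (m = 10, ICC 0.05) or 0.57 (m = 20, ICC 0.05), above the 0.5 target. At 1000 pairs the widest case is 2 × 0.160 = 0.32, well inside it.

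**The case against.** The strongest reply is that nothing in the SAP shows the interval to be too narrow. It reports no ICC, number of clinics or patients per clinic. BOA has been "offered at primary care clinics in Sweden since 2008" and its register holds more than 100,000 people. At 1000 pairs, m = 20 would mean that all matched BOA patients came from 1000/20 = 50 clinics. At m = 3 the widening is only 0.5% to 2.5%. This stands: the upper end of the range is a bound under assumptions, not an expectation.

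Second, the figure of about 630 illustrates precision with a hypothetical RCT, and the cohort is more than three times that size. This also stands. Missing the 0.5 target in Step 4 is no failure of the actual study.

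Third, a reader might infer that the equivalence claim itself is unsafe. The documents do not support that. They tie no interval to the 1-point bound, and with a half-width of 0.13 to 0.16 against a margin of 1, nearly every possible result gives the same verdict.

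Fourth, a reader might infer further sharing, such as common staff or education given in groups. The SAP mentions no treating staff, and it attaches the word group only to the exercise sessions. Nor does it show that the attendance criterion raises the correlation.

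What survives is narrower. By the SAP's own account one arm is treated at clinics with group exercise, and every planned analysis ignores this.

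**Conclusion.** The point holds as a modest one. Independence is doubtful in the face-to-face arm, and the gap lies in the t-test and in all three regressions, not in the t-test alone. If several matched patients share a clinic and the ICC is positive, the reported 95% interval is likely somewhat too narrow. Over the assumed range it should be 0.5% to 21% wider. The 21% is the widening needed; the corresponding understatement of the standard error is 18%.

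The size rests on the assumed ICC and patients per clinic. The regressions on unmatched patients were not sized, because the SAP gives neither the arm sizes nor the clinic sizes there. The estimated difference is unaffected and the equivalence verdict almost never changes, so this is a cheap improvement and no threat to the study's conclusion.

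**What to change.** Keep the point estimate and change only the variance.

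- Add the BOA clinic identifier to the data extraction, if the register holds it. Table 1 does not list it, so this has to be checked.
- In the matched analysis, with and without baseline adjustment, compute the interval with standard errors clustered on the clinic of the BOA member of each pair. Pairs that share a BOA clinic form one cluster, which also respects the pairing.
- In the unmatched regressions (sensitivity and missing-data fallback), cluster on clinic and let each digital patient be their own cluster.
- If the identifier is not held, label the interval as assuming independence and show its width over a stated range of ICCs.
- State which interval is compared with the 1-point bound, so that the corrected one is used.

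The cost is one more field, one variance option and a slightly wider interval.
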